Pivotal Trial of WaveLight® EX500 Excimer Laser System for the Correction of Myopia with and without Astigmatism Using InnovEyesTM in Conjunction with InnovEyesTM sightmap

STUDY ID RFP911-C001

STATISTICAL ANALYSIS PLAN

NCT04219891

Short Title:

Statistical Analysis Plan RFP911-C001

Full Title:

Statistical Analysis Plan RFP911-C001

Protocol Title: Pivotal Trial of WaveLight EX500 excimer laser system for the

correction of myopia with and without astigmatism using InnovEyesTM in conjunction with InnovEyesTM sightmap

This is Version 8.0 of the Statistical Analysis Plan for this study. This version of the Statistical Analysis Plan is based on Version 6.0 of the study protocol.

Document ID: V-CLN-0000922

Status: Approved, Version: 4.0 Page 2 of 56 Approved Date: 30 Nov 2022

Executive Summary:

Key Objectives:

The primary objective of the study is to evaluate the effectiveness and safety of the WaveLight EX500 excimer laser system for the correction of myopia with and without astigmatism using InnovEyes in conjunction with InnovEyes sightmap.

[figure not shown]
Decision Criteria for Study Success:

The effectiveness criteria will be considered to have been met if the percentage meets or exceeds the target rate at the time of refractive stability for all primary effectiveness endpoints.

The safety criteria will be considered to have been met if the percentage is less than the target rate at the time of refractive stability for all of the primary safety endpoints.

Table of Contents

Sta	atistical Ar	nalysis Plan RFP911-C0011
Ta	ble of Con	tents3
Lis	st of Table	s7
1	STUDY	OBJECTIVES AND DESIGN8
	1.1	Study Objectives8
	1.2	Study Description8
	1.3	Randomization8
	1.4	Masking8
	1.5	Interim Analysis8
2	ANALYS	SIS SETS9
	2.1	Safety Analysis Set
	2.2	Full Analysis Set
	2.3	Consistent Cohort Analysis Set
3	SUBJEC	T CHARACTERISTICS AND STUDY CONDUCT SUMMARIES9
4	REFRAC	CTIVE STABILITY9
5	EFFECT	IVENESS ANALYSIS STRATEGY10
	5.1	Analysis of Primary Effectiveness Endpoints

1 STUDY OBJECTIVES AND DESIGN

1.1 Study Objectives

The primary objective of the study is to evaluate the effectiveness and safety of the WaveLight EX500 excimer laser system for the correction of myopia with and without astigmatism using InnovEyes in conjunction with InnovEyes sightmap.

1.2 Study Description

This is a prospective, single-arm, multi-center, interventional study with planned bilateral InnovEyes LASIK treatment for subjects requiring refractive correction of myopia with or without astigmatism. All treated eyes will be targeted for emmetropia based upon the InnovEyes sightmap Measured Refraction. The postoperative state of each treated eye will be compared to the preoperative state of the same eye.

Subjects will be evaluated initially for suitability as candidates for bilateral LASIK. Potential subjects willing to participate will be consented and screened. Approximately 187 qualified subjects (up to 374 eyes) will receive bilateral InnovEyes LASIK and be followed for 1 year. Total duration of subject participation is approximately 1 year and includes 9 study visits consisting of Screening, Surgery, 1 day, 1 week, 1 month, 3 month, 6 months, 9 months, and 12 months. Subjects will be enrolled with intent to treat at least 20 eyes in each spherical diopter and each cylindrical diopter range (with only 10 eyes in the highest cylinder bin). Approximately 10 US study sites will participate in this clinical study. It is estimated that enrollment and follow-up of all subjects will take approximately 22 months.

The schedule of study procedures and assessments can be found in Section 10, Appendix – Schedule of Study Procedures and Assessments.

1.3 Randomization

This study is not randomized.

1.4 Masking

This is an open-label study with only WaveLight EX500 excimer laser system using InnovEyes in conjunction with InnovEyes sightmap.

1.5 Interim Analysis

An analysis will be performed once refractive stability is achieved; a final analysis will be performed once the one year follow up is complete.

2 ANALYSIS SETS

All eligible subjects will be screened to determine if they meet all inclusion and no exclusion criteria. Subjects who provide informed consent will be considered enrolled in the study. Evaluability of all subjects will be determined before database lock.

2.1 Safety Analysis Set

The safety analysis set (SAF) will contain all eyes that undergo surgery or attempted surgery (defined as eye drops given for flap treatment); the SAF will be the primary analysis set for the safety analysis.

2.2 Full Analysis Set

The full analysis set (FAS) will contain all eyes that successfully undergo surgery; the FAS will be the primary analysis set for the effectiveness analyses.

2.3 Consistent Cohort Analysis Set

The consistent cohort (CC) will contain all eyes in the FAS that have manifest refraction data at all post-operative visits from one month up to and including the visit where refractive stability is established. The CC will be the primary analysis set for the refractive stability analyses.

3 SUBJECT CHARACTERISTICS AND STUDY CONDUCT SUMMARIES

Subject characteristics and study conduct summaries include tables and listings such as a subject disposition table, demographics, and baseline characteristics tables (including age, gender, race, and ethnicity; visual acuity, manifest refraction, InnovEyes sightmap measured refraction, and pupil size), listing of screen failures by reason, and listing of subjects excluded from key analysis sets. All descriptive summary statistics will be displayed with n and % for categorical data, and with mean, standard deviation, median, minimum, and maximum for continuous data. Demographic and baseline characteristics will be summarized for the FAS.

4 REFRACTIVE STABILITY

Stability analyses will be performed on eyes that have every follow-up exam from 1-month up to the stability time point (the CC), as well as on the eyes that have 2 consecutive exams, but not necessarily every follow-up exam. The following stability analyses will be performed for the time intervals between all consecutive pairs of scheduled postoperative refractions:

- Percentage of eyes that achieve:
 - o a change of less than or equal to 1.00 D of MRSE between two refractions performed at 1 month and 3 months, and between subsequent refractions performed at least 3 months apart;
 - o a change of less than or equal to 0.50 D of MRSE between two refractions performed at 1 month and 3 months, and between subsequent refractions performed at least 3 months apart;
- Mean overall change and change per month in MRSE between consecutive scheduled visits as determined by a paired analysis;
- Mean \pm SD MRSE for the preoperative and each postoperative visit;
- Assessment of cylinder stability for correction of spherocylindrical refractive errors;

Refractive stability is achieved at the latter of two postoperative manifest refractions performed at least 3 months apart or at 3 months after surgery when compared with the 1-month interval, when all of the following recommended criteria are met:

- At least 95% of the treated eyes have a change ≤ 1.00 D of MRSE between the 2 refractions;
- The mean rate of change in MRSE, as determined by a paired analysis, is ≤ 0.5 D per year (0.04 D/month) over the same time period;
- The mean rate of change of MRSE decreases monotonically over time, with a projected asymptote of zero or a rate of change attributable to normal aging;
- The 95% confidence interval for the mean rate of change in MRSE includes zero or a rate of change attributable to normal aging; and
- Stability is confirmed at least 3 months after the stability time point by a statistically adequate subgroup (at least 80% of the cohort).

The primary safety and effectiveness endpoints for the study can only be evaluated once refractive stability has been established within the CC, as well as on the eyes that had 2 consecutive exams, but not necessarily every follow-up exam.

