10 STUDY PROCEDURES AND ASSESSMENTS

Study specific assessments will be obtained, including baseline prior to InnovEyes LASIK and postoperatively at the study visits outlined below (where A denotes the visit for the 2nd eye treated):

- Screening Visit 0 [-30 to -1 day prior to treatment]
- Visit 00 / Visit 00A [Day 0 surgery]
- Visit 1 / Visit 1A [Day 1]
- Visit 2 / Visit 2A [Day 5 to 9]
- Visit 3 / Visit 3A [Day 21 to 35]
- Visit 4 / Visit 4A [Day 70 to 98]
- Visit 5 / Visit 5A [Day 147 to 182]
- Visit 6 / Visit 6A [Day 245 to 301]
- Visit 7 / Visit 7A [Day 330 to 420]

In addition to the scheduled visits listed above, the following visits may apply as needed:

- Early Exit [completed when a treated subject reports they wish to discontinue study participation, if subject is willing]
- Unscheduled Visit [completed when a treated subject reports for additional follow-up]

Clinical assessments to be obtained at study visits are outlined in *Table 3–1* and are defined in the sections below.

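### The 95% CI that SAP 4 requires for refractive stability is built on about two eyes per subject, with no visible allowance for fellow-eye correlation; the resulting error is conservative

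*SAP*

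**What the plan says.** SAP 4 declares stability when five criteria hold together:

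1. At least 95% of treated eyes change by no more than 1.00 D of MRSE.
2. The mean rate of change is at most 0.5 D per year (0.04 D/month).
3. "The mean rate of change of MRSE decreases monotonically over time, with a projected asymptote of zero", or to an aging rate.
4. "The 95% confidence interval for the mean rate of change in MRSE includes zero or a rate of change attributable to normal aging".
5. At least 80% of the cohort confirms stability 3 months or more later.

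Protocol 6.4 and 12.4 list the same five. Stability is a gate: "The primary safety and effectiveness endpoints for the study can only be evaluated once refractive stability has been established within the CC".

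The unit is the eye. SAP 2.3: "The consistent cohort (CC) will contain all eyes in the FAS that have manifest refraction data" at every visit from one month to the stability visit. SAP 1.2: "Approximately 187 qualified subjects (up to 374 eyes) will receive bilateral InnovEyes LASIK".

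The only method wording is in SAP 4: "Mean overall change and change per month in MRSE between consecutive scheduled visits as determined by a paired analysis". Nothing visible mentions fellow eyes, clustering, a mixed model, GEE or a subject-level method. SAP 4 reads as continuous text, but parts of SAP 5 and 6 and the later appendices are withheld from the public copy.

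Separately, SAP 7, Protocol 12.9 and the synopsis (Protocol 3) attach a probability of about 95% to seeing a 1% ocular serious event at least once among 374 treated eyes.

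**The concern.** Pairing one visit with the next removes the level of each eye. It does nothing about the two eyes of one person changing together. If both eyes tend to drift the same way, 374 eyes carry less information than 374 independent observations, and a standard error computed over eyes is too small.

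The interval feeds a required criterion, and no hypothesis test is planned for the primary endpoints, so this is the one inferential rule in the visible text. A wrong failure at the 1-to-3-month interval moves stability from Visit 4 to Visit 5 at the earliest and confirmation from Visit 5 to Visit 6. Protocol 7.1 ties the main analysis, and a possible marketing application, to that confirmation.

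The study is also open-label, with the sponsor unmasked (Protocol 9.4). The correct interval is the wider one and is easier to pass, so adopting it after the data are seen would look self-serving. Naming it in advance avoids that.

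**Working it through.** **The plan's own figure.** The documents give no number for the stability interval. Their one computed design figure is the detection probability, 1 − 0.99^n for independent eyes:

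| Eyes | Source | Probability |
|---|---|---|
| 374 | SAP 7, as written | 97.7% |
| 337 | 374 less the 10% loss in Protocol 8 | 96.6% |
| 300 | follow-up floor in Protocol 8 | 95.1% |

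The stated 95% is reached at ln(0.05)/ln(0.99) = 298.1 eyes. It therefore belongs to about 300 followed eyes, not 374 treated eyes. For 187 pairs with p = 0.01 and an assumed within-pair correlation c of the event, the probability is 1 − [(1−p)² + c·p(1−p)]^187, which gives 95.9% at c = 0.3 and 94.0% at c = 0.5.

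**Width of the stability interval.** Inputs: 374/187 = 2.0 eyes per subject (SAP 1.2); a 95% interval, taken as two-sided because sidedness is not stated; r assumed.

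- With n eyes including m complete pairs, Var(mean) = (SD²/n)(1 + 2mr/n). If every subject contributes two eyes, 2m/n = 1 and the true standard error is sqrt(1 + r) times the eye-level one. Subjects with one eye in the set reduce the factor.
- At a true rate of zero, P(eye-level interval excludes zero) = 2[1 − Φ(1.96/sqrt(1 + r))].

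| Assumed r | sqrt(1 + r) | P(excludes zero) | One tail |
|---|---|---|---|
| 0 | 1.00 | 5.0% | 2.5% |
| 0.1 | 1.05 | 6.2% | 3.1% |
| 0.3 | 1.14 | 8.6% | 4.3% |
| 0.5 | 1.22 | 11.0% | 5.5% |
| 0.8 | 1.34 | 14.4% | 7.2% |

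Criterion 4 also passes if the interval includes an aging rate. With a true rate of zero, that can rescue misses on one side only, so the wrong-failure rate lies between the last two columns. A simulation of 187 bilateral subjects (20,000 runs) gave 8.7%, 11.0% and 14.4% at r = 0.3, 0.5 and 0.8 for the eye-level interval, and 5.0%, 5.0% and 5.4% for GEE with robust standard errors.

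**In diopters per month.** Window mid-points in Protocol 10 are Day 28 (Visit 3) and Day 84 (Visit 4): 56 days, or 1.84 months. Half-width at eye level = 1.96·SD/sqrt(374)/1.84; the clustered value at r = 0.5 is sqrt(1.5) times that. The SD of the change is assumed.

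| Assumed SD of change | Eye level | Clustered, r = 0.5 |
|---|---|---|
| 0.25 D | 0.014 | 0.017 |
| 0.35 D | 0.019 | 0.024 |
| 0.50 D | 0.028 | 0.034 |

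An observed mean rate between the two values in a row would include or exclude zero according to the method. At r = 0.1 and SD 0.35 D that zone shrinks to 0.0193–0.0202 D/month (0.0193 × 1.049).

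**Direction.** With an identity link and an independence working correlation, both intervals have the same centre, and the eye-level one lies inside the clustered one. Any result that passes criterion 4 at eye level also passes when clustered.

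**Delay.** Mid-points of Visits 4, 5 and 6 are Days 84, 164.5 and 273. Stability would move by 80.5 days and confirmation by 108.5 days.

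**The case against.** The strongest reply is that the error costs little and runs against the sponsor. It can only withhold or delay, subjects are followed to 12 months anyway, and the primary endpoints are descriptive percentages against targets. That stands, and it makes this a correction to the plan rather than a threat to its conclusions.

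The size is also uncertain. The relevant r is for the change in MRSE, not its level; differencing within an eye removes stable features shared by the two eyes, so r could be low. At r = 0.1 the excess is about one percentage point. That stands too.

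A reader might infer from the D/month table that this interval would decide the stability verdict, because all those rates lie under the 0.04 D/month limit. The documents do not support that: criteria 1, 3 and 5 must also hold, and the interval may include an aging rate instead of zero. The visible text puts no number on that rate, and naming a standard-error method does not settle it.

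A method may also sit on withheld SAP pages, or the cited ANSI standard may bear on it. This limits confidence. It does not remove the point, because SAP 4 itself neither states a method nor points to one.

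**Conclusion.** The point holds in a limited form. If the visible wording is applied at eye level, the required interval is too narrow by up to sqrt(1 + r) for any positive r. At a true rate of zero it excludes zero in about 6% to 14% of cases for r between 0.1 and 0.8, instead of 5%. Both r and the SD of change are assumptions, and two eyes per subject is the upper case.

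Three stronger readings are not supported:

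- *That the plan makes false stability more likely.* The narrow interval makes criterion 4 harder to meet, and the other four criteria apply regardless.
- *That every exclusion of zero is an error.* Criterion 3 allows a nonzero early rate. If the true rate is neither zero nor the aging rate, an interval that excludes both is a correct failure.
- *That the sample size falls short.* Under independence the detection statement understates what 374 eyes provide; it needs rewording, not more eyes.

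Nor is the omission wholly neutral for the co-primary endpoints. It does not distort a percentage at a given visit, but a wrong failure changes the visit at which those percentages are read.

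**What to change.** In SAP 4, with Protocol 6.4 and 12.4 following by reference, add:

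> *The mean rate of change in MRSE and the two-sided 95% CI used for the stability criterion will be estimated with subject as the cluster, for example by GEE with an identity link and robust standard errors.*

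An equivalent subject-level method, such as a mixed model or a subject-level bootstrap, would serve as well, provided one is named. If a withheld section already specifies the method, a cross-reference in SAP 4 is enough.

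Minor: in SAP 7, Protocol 12.9 and the synopsis, restate the detection probability as about 97.7% for 374 eyes and about 95% for 300 followed eyes, both assuming independent eyes, and somewhat lower if fellow eyes are positively correlated. No assumed correlation should be written in as fact.

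The cost is one sentence and one standard procedure, with no extra data, subjects or enrolment. The wider interval makes criterion 4 somewhat easier to meet; the other four criteria are unchanged.

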Refractive stability is said to have been achieved at the latter of two postoperative manifest refractions performed at least 3 months apart (or at 3 months after surgery when compared with the 1-month visit) if all the requirements for stability listed in the endpoints section of the synopsis have been met. Stability will be confirmed by an adequate subgroup (at least 80% of the cohort) at the next scheduled visit interval.

The number and percentage of eyes meeting each of the primary effectiveness endpoints will be calculated. The effectiveness criteria will be considered to have been met if the percentage meets or exceeds the target rate at the time of refractive stability for all primary effectiveness endpoints.

The number and percentage of eyes experiencing each of the primary safety endpoints will also be calculated. The safety criteria will be considered to have been met if the percentage is less than the target rate at the time of refractive stability for all of the primary safety endpoints.

An analysis will be performed once refractive stability is achieved; a final analysis will be performed once the one-year follow-up is complete.

	Up to 374 eyes will be treated in this study. With 374 eyes treated, any ocular serious adverse event type that occurs in at least 1% of the population undergoing the procedure will be observed in this study at least one time, with approximately 95% probability. This is in accordance with ANSI Z80.11-2012(R2017).
Key Words	LASIKRay TracingMyopiaAstigmatism
Associated Materials	 WaveLight® EX500 Laser System WaveLight® FS200 Laser System Patient Interface for WaveLight FS200 Laser System WaveCard

Table 3–1 Schedule of Study Procedures and Assessments

		Screening ¹	Surgery	Surgery Postoperative								er
		Visit 0	Visit 00 / Visit 00A ²	Visit 1 / Visit 1A	Visit 2 / Visit 2A	Visit 3 / Visit 3A	Visit 4 / Visit 4A	Visit 5 / Visit 5A	Visit 6 / Visit 6A	Visit 7 / Visit 7A	Early Exit	USV ³
Proce	edure/ Assessment	Day -30 to -1	Day 0	Day 1	Day 5 to 9	Day 21 to 35	Day 70 to 98	Day 147 to 182	Day 245 to 301	Day 330 to 420		
Inform	med Consent	X										
Inclusion/Exclusion		X	X^4									
Demographics		X										
Medic	cal History	X										
Concomitant Medications		X	X	X	X	X	X	X	X	X	X	X
Urine	Pregnancy Test ⁵ *	X										
Cyclo	plegic Refraction	X						X				
Mesopic pupil size		X				X	X	X	X	X	X	
	Aberrometry	X^6				X	X	X	X	X	X	
lap	Biometry	X^6				X	X	X	X	X	X	
ghtn	Keratometry	X^6				X	X	X	X	X	X	

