7 INVESTIGATIONAL PLAN

7.1 Study Design

This is a prospective, single-arm, multi-center, interventional study with planned bilateral InnovEyes LASIK treatment for subjects requiring refractive correction of myopia with or without astigmatism. All treated eyes will be targeted for emmetropia. The postoperative state of each treated eye will be compared to the preoperative state of the same eye.

Subjects will be evaluated initially for suitability as candidates for bilateral LASIK. Potential subjects willing to participate will be consented and screened. Approximately 187 qualified subjects (up to 374 eyes) will receive bilateral InnovEyes LASIK and be followed for 1 year. Total duration of subject participation is approximately 1 year and includes 9 study visits consisting of Screening, Surgery, 1 day, 1 week, 1 month, 3 month, 6 months, 9 months, and

12 months. Subjects will be enrolled with intent to treat at least 20 eyes in each spherical diopter and each cylindrical diopter range (with only 10 eyes in the highest cylinder bin). Approximately 10 US study sites will participate in this clinical study. It is estimated that enrollment and follow-up of all subjects will take approximately 22 months. Additional information on the study population can be found in Section 8.

Assessments will be obtained at baseline and at appropriate times after InnovEyes LASIK to evaluate the safety and effectiveness of the treatment.

The main analyses for effectiveness and safety will be conducted when refractive stability for the cohort has been determined and 80% of the eyes in the cohort have completed the next scheduled visit after refractive stability (Refractive Stability is defined in Section 6.4 and 12.4). The Sponsor may file a Pre-Market Approval application once this analysis is complete. Subjects are followed for at least 12 months (Day 330 to Day 420) for safety and supportive effectiveness assessments. Final data analyses will be conducted at study completion.

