7.2.1 Purpose and Timing of Interim Analyses and Resulting Design Adaptations

Analysis will occur for review of refractive stability as specified by ANSI Z80.11-2012(R2017), which includes 1 additional visit beyond stability completed by at least 80% of the cohort.

No changes to study design, after the initiation of the study, are planned.

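### Does the missing pass rule for confirming refractive stability leave the gate to the primary endpoints undefined?

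*SAP*

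**What the plan says.** SAP 4, and Protocol 6.4 and 12.4 in the same terms, list five criteria that must all hold. In short: (1) at least 95% of eyes change by no more than 1.00 D; (2) the mean rate is at most 0.5 D per year; (3) "The mean rate of change of MRSE decreases monotonically over time"; (4) the 95% interval for the mean rate covers zero or an ageing rate; (5) "Stability is confirmed at least 3 months after the stability time point by a statistically adequate subgroup (at least 80% of the cohort"). The gate follows: "The primary safety and effectiveness endpoints for the study can only be evaluated once refractive stability has been established within the CC".

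Three other places in the Protocol touch the fifth criterion.

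- The synopsis (Protocol 3): "Stability will be confirmed by an adequate subgroup (at least 80% of the cohort) at the next scheduled visit interval".
- Protocol 7.1 places the main analyses after stability has been determined and "80% of the eyes in the cohort have completed the next scheduled visit after refractive stability", and refers to 6.4 and 12.4 for the definition.
- Protocol 7.2.1 describes the stability review as including "1 additional visit beyond stability completed by at least 80% of the cohort", and attributes this to the cited ANSI standard.

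The visit windows are in Protocol 10: "Visit 4 / Visit 4A [Day 70 to 98"] for the 3-month visit and "Visit 5 / Visit 5A [Day 147 to 182"] for the 6-month visit.

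**The concern.** The fifth criterion has a verb but no test. Three rules can be read into the text:

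- **Completion only:** 80% of the cohort have attended the next visit.
- **Criteria re-met:** criteria 1, 2 and 4 hold again over the confirming interval.
- **Re-met with monotonicity:** as above, with criterion 3 also carried through that interval.

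These can give different answers. Completion only would pass a cohort that is stable to 3 months and then drifts faster than the plan's own limit. The strictest rule would often fail a cohort with no drift, which then could not meet the effectiveness criteria for that reason alone.

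The timing also looks inconsistent, since a minimum of 3 months after a visit and the next visit need not coincide in days. The study is open-label with no data monitoring committee, and Protocol 7.1 links a possible marketing application to this analysis. A rule chosen with the interval results in view would be open to criticism.

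**Working it through.** **The plan's own figure.** 0.5 D/year ÷ 12 = 0.0417 D/month, which matches the stated 0.04.

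**Timing.** The gap from the 3-month to the 6-month visit runs from 147 − 98 = 49 to 182 − 70 = 112 days; between window midpoints it is 164.5 − 84 = 80.5 days. Of the 29 × 36 = 1,044 possible day pairs, 253 (24%) are at least 91 days apart. Counted in days, 80% could not be reached if visits are spread evenly. But SAP 4 applies the same 3-month spacing to the stability intervals themselves, over all consecutive scheduled refractions. A day count would disqualify the 3-to-6-month interval for most eyes. Only visit labels (3, 6, 9, 12 months) make the definition workable, and by label the wordings agree.

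**The 80%.** With the 10% loss expected in Protocol 8, attendance is 90%. If 95% of those eyes are individually stable, 0.90 × 0.95 = 85.5%. The threshold is passed whether it means eyes seen or eyes stable. The two differ only when attendance lies between 80% and 0.80/0.95 = 84.2%.

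**The pass rule.** The documents give no SD, correlation or drift, so these are assumptions: 187 × 0.9 ≈ 168 subjects with two eyes each, visits at window midpoints, SD 0.20 D per visit, fellow-eye correlation 0.5, ageing rate zero, criterion 3 strict. Simulated results:

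| Scenario | Completion only | Re-met | Re-met with monotonicity |
|---|---|---|---|
| No drift, never declared stable | 0.5% | 8–9% | 42% |
| Early drift 0.02 D/month, halving each interval, never declared | 4% | 41% | 63% |
| Drift 0.05–0.08 D/month from 3 months on, declared at 3 months | 89% | at most 0.1% | at most 0.1% |

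The no-drift row barely moves for SD 0.10 to 0.30 D.

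**What drives these figures.**

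- The 42% comes from requiring the point estimate to fall in every interval. With a tolerance of 0.01 D/month it is about 6%.
- The 8–9% reflects an interval that treats fellow eyes as independent. With a subject-level interval it is 3.8%; the SAP says only that the analysis is paired.
- The 0.5% requires criterion 3 to be empty at 3 months. If the 1-week refraction counts as the start of the sequence, which is arguable, it becomes 21%.

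**The obvious substitute.** Suppose confirmation required 80% completion plus criteria 1 and 2 met again, with 3 and 4 judged only up to the stability visit. The interval is 80.5/30.44 = 2.645 months. The eye-level standard error of the rate is 0.20 × √2 / √336 / 2.645 = 0.00583 D/month. Allowing for correlation, the true standard error is 0.00583 × √1.5 = 0.00715.

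- Criterion 4 passes at 3 months with no drift: 2Φ(1.96/√1.5) − 1 = 0.890.
- Later drift 0.03, substitute: Φ((0.0417 − 0.03)/0.00715) = Φ(1.63) = 0.949; × 0.890 = 0.84.
- Later drift 0.04, substitute: Φ((0.0417 − 0.04)/0.00715) = Φ(0.23) = 0.592; × 0.890 = 0.53.
- Later drift 0.03, criteria re-met (criterion 4 half-width 1.96 × 0.00583 = 0.0114): Φ((0.0114 − 0.03)/0.00715) = Φ(−2.60) = 0.005; × 0.890 = 0.004.

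The products treat successive intervals as independent, though they share a refraction. Full simulation gives 85%, 53–55% and 0.2–0.3%. The substitute therefore keeps stable cohorts (0.5% undeclared) by letting moderate late drift through.

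**The case for a change.** The strongest case for a change is that the gap is real and sits on a gate. The three rules differ sharply when drift starts after the stability visit, every refraction needed is already collected, and agreeing the wording before the data are reviewed would cost little.

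Part of this stands: the visible text does not say which criteria the confirming eyes must meet, and in some cases that could delay or alter the declaration of stability. Three things limit it.

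- The 89% for late drift needs completion alone to count as confirmation. That reading empties the verb in the fifth criterion, and Protocol 7.1 does not support it: it asks for stability to have been determined and, separately, for 80% to have completed the next visit.
- Late drift would not be hidden. SAP 4 requires the mean change, the change per month and the percentages within 0.50 and 1.00 D for every consecutive pair of visits.
- The reading governs when, and sometimes whether, the percentages are compared with their targets. It does not alter how they are calculated, and no co-primary result has been shown to move across its target. No hypothesis test is planned, and a one-year summary is produced in addition.

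The cited standard, the Manual of Procedures, the Deviation and Evaluability Plan and the redacted SAP pages may say more; the conclusion does not rely on them.

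**Conclusion.** This is an unwritten detail, not a stated rule that gives a wrong result. The definition is consistent across SAP 4 and Protocol 6.4 and 12.4. Protocol 7.1 and 7.2.1 deal with analysis timing, and the synopsis agrees with the definition by visit label. An analyst would check, in the at least 80% of the cohort seen at the next labelled visit, that the stability criteria still hold. On that reading a cohort with no drift goes undeclared in about 4 to 9% of trials, depending on how fellow eyes are handled, and drift above the plan's own limit after 3 months is almost never declared stable at 3 months.

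Spelling out a different rule would be a choice between errors: leaving criterion 4 out of confirmation lowers the failure rate for stable cohorts to 0.5% but passes later drift of 0.03 and 0.04 D/month in about 85% and 53–55% of trials. Nothing in the documents shows that to be better. All these percentages rest on the assumed SD, correlation, drift pattern and zero ageing rate; the timing arithmetic rests only on the visit windows, with even spread assumed for the 24%. No change to the plan is called for.
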